5.2.4. Quizartinib Dose Reduction with Strong CYP3A4 Inhibitors

Data from Study AC220-015, which examined the effect of strong and moderate CYP3A4 inhibitors on quizartinib PK in human volunteers, show that concomitant ketoconazole, a strong

CYP3A4 inhibitor, increased quizartinib AUC_{0-inf} and steady state C_{max} (after repeat daily dosing) approximately 2-fold, and concomitant fluconazole, a moderate CYP3A4 inhibitor, increased quizartinib AUC_{0-inf} and steady state C_{max} approximately 1.2-fold. Subjects receiving concomitant medication with a strong CYP3A4 inhibitor on Day 1, and who are randomized to quizartinib, will take 20 mg/day. Subjects who begin treatment with a strong CYP3A4 inhibitor while receiving quizartinib will be required to be reduced from either 60 mg/day to 30 mg/day or from 30 mg/day to 20 mg/day. If the subject discontinues the strong CYP3A4 inhibitor, the dose of quizartinib can be resumed at the prior dose. No dose reduction of quizartinib is required when subjects are co-administered a moderate or weak CYP3A4 inhibitor. See [Appendix 1: List of Potential QT Prolonging Drugs, CYP3A4 Inhibitors/Inducers, and P-glycoprotein Inhibitors/Inducers](#).

5.2.5. Treatment with Quizartinib Following HSCT

Allogeneic transplant has become an accepted standard of care for consolidating newly diagnosed FLT3-ITD AML subjects in first remission.^{10,11,12} Additionally, treatment consensus guidelines recommend HSCT for subjects with relapsed AML regardless of FLT3-ITD status whenever feasible. Based on data from the Phase 2 studies, approximately 35% of subjects will likely be bridged to HSCT in the Phase 3 AC220-007 Study.

The post-HSCT relapse rate for FLT3-ITD positive AML subjects is higher than that observed for other AML sub-groups undergoing consolidation HSCT, and the leukemia cells at relapse are typically highly addicted to FLT3-ITD signaling.¹³

The use of a TKI to induce remission and then as maintenance post-HSCT has been established in BCR-ABL acute lymphocytic leukemia (Ph+-ALL). In adults with Ph+ ALL, HSCT is an established treatment standard of care,¹⁴ and BCR-ABL TKIs are not only used to bridge patients to transplant, they are routinely used post-HSCT to maintain remission and prolong survival.^{15,16} In terms of AML, a FLT3 inhibitor (sorafenib) currently approved for other oncology indications has been reported to have activity in the post-HSCT setting.¹⁷ Given current standard practice with BCR-ABL TKIs in Ph+ ALL, for subjects randomized to the quizartinib treatment group, quizartinib will be offered to those subjects undergoing HSCT with the aim of reducing the high risk of relapse post-HSCT and to evaluate whether administration of quizartinib before HSCT and as maintenance following HSCT, is of clinical benefit.

A phase 1 study (A Phase 1 Study of AC220 [ASP2689] as Maintenance Therapy in Subjects with Acute Myeloid Leukemia who Have Been Treated with an Allogeneic Hematopoietic Stem Cell Transplant: 2689-CL-0011) enrolled 13 subjects who were in remission following an allogeneic HSCT. These subjects were identified as FLT3-ITD(+) at diagnosis, and after recovery of blood counts post-HSCT were treated with doses of 40 mg/day (n=7) and 60 mg/day (n=6) of quizartinib. Preliminary data have shown that both doses are well tolerated with 5/7 (71%) subjects in the 40 mg cohort and 6/6 (100%) subjects in the 60 mg cohort remaining on quizartinib without disease relapse. There were 8 subjects who discontinued treatment: (one due to progressive disease, two per the Investigator's discretion, four due to Serious Adverse Events (SAEs), and one for reasons that were not specified), with 10 of 13 subjects receiving quizartinib for more than 1 year.

5.3. Study Duration

Time from enrollment of first subject to the 280th event (death) should be approximately 36 months.

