TITLE: A Phase 3 Open-Label Randomized Study of Quizartinib Monotherapy Versus Salvage Chemotherapy in Subjects with FLT3-ITD Positive Acute Myeloid Leukemia (AML) Refractory To or Relapsed After First-line Treatment With or Without Hematopoietic Stem Cell Transplantation (HSCT) Consolidation		
INDICATION: Relapsed or refractory FLT3-ITD(+) AML		
STUDY PHASE: 3		
STUDY CENTERS: Approximately 150 centers globally		
NUMBER OF SUBJECTS PLANNED: Approximately 363 subjects will be randomized.		
STUDY DURATION: Approximately 36 months		
STUDY OBJECTIVES 
The primary objective of the study is to determine whether quizartinib monotherapy prolongs overall survival (OS) compared to salvage chemotherapy in subjects with FLT3-ITD positive AML who are refractory to or have relapsed within 6 months, after first-line AML therapy.
 
The secondary objective is to determine event-free survival (EFS) with quizartinib versus salvage chemotherapy.
 
Exploratory objectives are:
 
• to compare the composite complete remission (CRc = complete remission [CR] + complete remission with incomplete platelet recovery [CRp] + complete remission with incomplete hematologic recovery [CRi]) rate• to compare the complete remission (CR) rate• to compare the duration of composite complete remission (CRc)• to compare the duration of complete remission (CR)• to determine leukemia-free survival (LFS)• to compare the transplantation rate• to determine the QTc prolonging effects of quizartinib in relation to plasma drug concentrations• to determine the pharmacokinetics (PK) of quizartinib and its active metabolite, AC886• to determine the exposure-response relationship		

- to determine resource utilization in this study population
- to identify AML-associated mutations and their frequencies
- pharmacogenomic and pharmacoproteomic determinations

STUDY DESIGN

This is a Phase 3, randomized, open-label, 2-arm study to compare the effect of quizartinib monotherapy and salvage chemotherapy on OS in subjects with FLT3-ITD (+) AML that is refractory or relapsed within 6 months, after first-line therapy with or without consolidating hematopoietic stem cell transplantation (HSCT).

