3.3. Clinical Studies

A brief summary is given below. Refer to the current quizartinib [Investigator's Brochure](#) for additional information on clinical experience with quizartinib.

As of 22 Jan 2016, a total of 1289 subjects received quizartinib in 19 clinical studies including 624 subjects with either AML or solid tumors, 472 healthy volunteers, and 193 subjects with AML, ALL and MDS in 4 investigator sponsored trials.

Quizartinib was studied in 76 AML subjects in a Phase 1 study with intermittent dosing (14 days on drug followed by 14 days rest) from 12 mg to 450 mg, and continuous dosing at 200 mg and 300 mg.⁸ Plasma taken from subjects and assayed in an in vitro plasma inhibitory assay, showed maximal inhibition of FLT3-ITD signaling at 60 mg dose as early as 2 hours after the first dose. A marked reduction of FLT3-ITD phosphorylation in vivo was also observed at 60 mg and

higher doses. The overall response rate was 53% in FLT3-ITD(+) subjects and 14% in FLT3-ITD(-) subjects.

The response rate observed in Phase 1 was confirmed in the Phase 2, AC220-002 study of single agent quizartinib in relapsed or refractory AML. In this Phase 2 study a total of 333 subjects were enrolled in 2 cohorts; Cohort 1 included subjects 60 years or older who were relapsed or refractory to 1 line of therapy and Cohort 2 included subjects 18 years or older who were relapsed or refractory to salvage therapy or relapsed after HSCT. In Cohort 1, the CRc rate was 57% in FLT3-ITD(+) subjects with a median survival of 25.3 weeks.⁴ Cohort 2 showed a CRc rate of 46% in FLT3-ITD(+) subjects with a median survival of 24.0 weeks.⁵ Importantly, 35% of Cohort 2 FLT3-ITD(+) subjects were bridged to HSCT. Almost all (94%) subjects proceeding to HSCT had achieved a CRc or partial remission (PR) on quizartinib and their 1 year survival rate was 39%.

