13.3. Sample Size Determination

Calculation of sample size is based on comparison of OS, the primary efficacy endpoint, in the 2 treatment groups (quizartinib and salvage chemotherapy) at a 2-sided significance level of 0.05, assuming that median survival is 3.9 months in the salvage chemotherapy group with an increase to 6 months, in the quizartinib group (hazard ratio 0.65). A total of 280 events (deaths) are necessary to meet a power requirement of 90%, given an interim analysis planned at 140 events (deaths) with O'Brien-Fleming boundary for superior efficacy and a conditional power (CP) of 10% for futility. For the purpose of sample size calculation, subjects are assumed to be accrued at a rate of 19.2 per month with a drop-out rate of 10%. The target accrual is a total of approximately 363 subjects randomized in a 2:1 ratio (242 subjects in the quizartinib group and 121 in the salvage chemotherapy group) over 17 months, to reach required number of events in a reasonable timeframe and to compensate for drop-outs. All calculations for sample size were performed using East® 6.3.

One formal interim analysis will be performed by an independent SAC and evaluated by an independent DMC according to statistical procedures defined a priori. At the interim analysis, the DMC may recommend 3 potential study options: (1) the study should be stopped due to futility; (2) the study should be stopped for superior efficacy in the quizartinib arm; or (3) the study should continue as planned to the total targeted number of 280 events.

It will be impossible to blind treatment allocations for individual subjects because of different treatment administration schedules and adverse events between the 2 study arms. However, the primary endpoint of survival is a robust endpoint and not susceptible to bias resulting from lack of blinding. Additionally, the Sponsor will not have access to aggregate efficacy data except when data from both treatment and control arms are combined. In addition, data relating to the primary endpoint of survival will be restricted so that the Sponsor will not have access to follow up data on individual subjects after 30 days of discontinuing study treatment. Approximately 80% of events will occur in this long term follow up period and so the Sponsor will be blinded to the primary endpoint of the study.

Randomization will be stratified by prior therapy and response, and pre-selected salvage chemotherapy:

Prior therapy and response:

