13.4. Primary Efficacy Analysis

Primary efficacy analysis will take place after the required number of events (deaths), 140 events (deaths) at the interim analysis or 280 events (deaths) at the final analysis, has occurred.

The primary efficacy endpoint (OS) analysis will be based on the stratified log-rank test. The stratification factors will be those used for randomization. A non-stratified log-rank test will be used as supportive evidence of efficacy. These analyses will be performed on the intent-to-treat (ITT) analysis data set, consisting of data from all subjects randomized.

Kaplan-Meier methods will be used to estimate OS in each treatment group, both overall and within subsets of subjects defined by the stratification factors. Estimates of median survival will be provided with 95% confidence intervals. Hazard ratio estimates will also be presented.

Overall survival will be censored at the last date when subjects were known to be alive. For primary analysis, overall survival will not be censored at the time of subsequent non protocol AML therapy, including transplantation.

Sensitivity analyses of OS will be performed by implementing an additional censoring rule: censoring at the date of HSCT for all subjects who have undergone HSCT. The sensitivity analyses will be described in detail in the statistical analysis plan. The primary efficacy analysis will be repeated for the per protocol set (PPS), which includes all subjects who are randomized and have no major protocol deviations.

Protocol deviations will be reviewed in a blinded fashion and categorized as major or minor before the interim analysis and data base lock and will be documented in a memo.

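### Does the gap between the stated 36 months and the 21–26 months implied by the design inputs put the 280-death final analysis at risk?

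*Combined protocol and SAP*

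**What the plan says.** Section 5.3 gives the timing: "Time from enrollment of first subject to the 280th event (death) should be approximately 36 months". The synopsis agrees ("STUDY DURATION: Approximately 36 months").

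Section 13.3 sizes the trial "at a 2-sided significance level of 0.05" for 90% power at a hazard ratio of 0.65 (medians 3.9 and 6 months), with 280 deaths and one interim look at 140. For recruitment, "subjects are assumed to be accrued at a rate of 19.2 per month with a drop-out rate of 10" per cent, and 363 subjects are to be randomized 2:1 over 17 months. The drop-out rate has no time unit.

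The final analysis is timed by deaths alone. Section 13.4 places the primary analysis after "140 events (deaths) at the interim analysis or 280 events (deaths) at the final analysis, has occurred". Section 13.3 says that, absent early stopping, "the study should continue as planned to the total targeted number of 280 events". The supplied text has no calendar cut-off and no rule for a final count below 280. Section 13.10 sets the efficacy boundary with a Lan-DeMets O'Brien-Fleming spending function.

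**The concern.** Two figures that should come from one calculation do not agree. The inputs in Section 13.3 give a date 10 to 15 months earlier than Section 5.3 does, and nothing explains the difference.

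Two unstated assumptions could close the gap. Slower accrual would only move the calendar. A plateau of long-term survivors would matter more, because a plateau large enough to delay the 280th death to month 36 leaves very few deaths to spare. If it were slightly larger, the trigger for the primary analysis would never be met, and a cut-off would have to be set late in an open-label trial. The protocol gives some reason to think of a plateau: "approximately 35% of subjects will likely be bridged to HSCT in the Phase 3 AC220-007 Study" (Section 5.2.5), and for transplanted Phase 2 subjects "their 1 year survival rate was 39" per cent (Section 3.3).

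**Working it through.** **1. The plan's own design figures.**
- Hazard ratio: 3.9/6 = 0.65.
- Fixed-design deaths at 2:1: (1.960 + 1.282)² / [(2/3)(1/3)(ln 0.65)²] = 255. With the Lan-DeMets O'Brien-Fleming boundary at half information (z = 2.963, then 1.969) and stopping at 10% conditional power under the current trend, 280 deaths give power 0.900.
- Subjects: 19.2 × 17 = 326.4, and 326.4/0.9 = 362.7, so 363. The 19.2 per month is therefore net of drop-out; gross accrual is 363/17 = 21.4 per month.

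All three reproduce.

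**2. Time to the 280th death.** With uniform accrual over A months and no drop-out, expected deaths by month T > A in an arm of n subjects are n × [1 − (e^(−λ(T−A)) − e^(−λT))/(λA)], where λ = ln 2/median. For A = 17 and T = 21.2 this gives about 177 on quizartinib (λ = 0.1155, n = 242) and 103 on control (λ = 0.1777, n = 121), a total of 280. The other readings are:

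| Reading of the 10% drop-out | 363 over 17 months | 363 over 18.9 months (363/19.2) | Deaths expected by month 36 |
|---|---|---|---|
| None | 21.2 | 22.5 | 350 / 348 |
| 10% per year | 22.4 | 23.8 | 330 / 329 |
| 10% overall, competing hazard | 23.5 | 24.8 | 319 / 317 |
| 10% contribute no death | 24.9 | 26.2 | 315 / 313 |

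No reading gives 36. Randomizing only 326 and then losing 10% gives about 31 to 34 months, but that counts drop-out twice and is not the stated sample size.

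**3. What would give 36 months.** Slower accrual does so at 9.8 to 11.3 per month, and 280 deaths are then still reached. A plateau does so if, with 10% contributing no death, about 12 to 13% of followed subjects are long-term survivors. The limit is 1 − 280/(0.9 × 363) = 14.3%. Keeping the hazard ratio at 0.65, with control plateau p and quizartinib plateau p^0.65, the limit solves 326.7 × [1 − (2/3)p^0.65 − p/3] = 280. That gives p = 7.1% and p^0.65 = 17.9%.

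**4. How often 280 would be missed.** Share of 4,000 simulated trials that ever reach 280 deaths, under assumed plateaus (the plan states none):

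| Drop-out reading | 6% control / 16% quizartinib | 7% / 18% |
|---|---|---|
| None | 100% | 100% |
| 10% per year | just under 100% | about 99% |
| 10% overall, competing hazard (0.0146 per month) | about 93% | about 83% |
| 10% contribute no death | 77% | 55% |

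The competing hazard d solves (2/3)d/(0.1155 + d) + (1/3)d/(0.1777 + d) = 0.10.

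**5. Is a plateau supported by the plan's figures?** 0.35 × 0.39 = 14% of quizartinib subjects transplanted and alive at one year. The plan's exponential curve leaves 0.5^(12/6) = 25% of that arm alive at 12 months, so 14% fits inside it. Comparing 14% at one year with the curve's 6% at 24 months or 2% at 36 sets different time points side by side.

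**6. Cost of a shortfall.** In the worst cell above (7%/18%, 10% contributing no death) the median final count is 281 deaths and the 5th percentile is 267. From Φ(|ln 0.65| × √(2D/9) − z), with the final boundary z recomputed at D deaths: 280 deaths (z = 1.969) give 92%, 270 (1.967) give 91%, and 250 (1.967) give 89%. This takes the final look alone, without the futility rule.

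**The case for a change.** The best case for a change is this. The mismatch is arithmetic and depends on no assumption about a tail. Its two natural explanations have very different consequences, and the reader cannot tell which applies. A plateau that yields month 36 leaves at most about 282 to 287 deaths ever observable. With plateaus of 6%/16% and 7%/18% and a tenth of subjects lost, 23% and 45% of trials never reach 280, and power falls from 93% to 80% and 68%. A few sentences would settle the matter at no cost in subjects.

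The mismatch stands, and so does the absence of a calendar rule in the supplied text (the Interim Analysis Plan and DMC charter, to which the protocol refers, were not available). The rest is weaker. The 23% and 45% use the harshest of four drop-out readings. For survival it is also the least natural one, because Sections 5.4.5 and 6.2.5.4 have sites trace vital status through public records even after consent is withdrawn. The intermediate reading still gives some failures (about 7% and 17%), but only with the assumed plateau. The power figures of 80% and 68% count every trial short of 280 as lost unless it crossed at the interim; analyzing the deaths available would cost 1 to 3 points.

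Late timing in an open-label trial is a fair worry, but Section 5.6.5 limits the sponsor to aggregate efficacy data with both arms combined, so a cut-off could be set on pooled death counts. Nor is a calendar fallback neutral: a rule of whichever comes first, with its time still to be chosen, could bring the analysis forward if accrual were slow and make 280 less than a firm target.

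**Conclusion.** The 36 months in Section 5.3 and the synopsis does not follow from Section 13.3, which implies about 21 to 26 months. This is a planning inconsistency of 10 to 15 months in a figure offered as approximate. Correcting it would change no test, boundary, event target, sample size or power. Under the plan's own assumptions even the harshest drop-out reading yields 0.9 × 363 = 327 deaths in the end, 47 more than needed, with 313 to 315 expected by month 36.

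A realistic chance of never reaching 280 deaths requires two things together: a survival plateau that the protocol neither states nor supports with data beyond one year, and loss of survival information on roughly a tenth of subjects. Should the count stall slightly below 280, the spending function already specified lets the final boundary be computed at the deaths observed, with power at a hazard ratio of 0.65 of 91% at 270 and 89% at 250. The missing time unit for drop-out and the net accrual rate are details that the arithmetic largely settles (362.7 rounds to 363). A written fallback would be optional good practice. The conclusion rests on exponential survival at the stated medians and uniform accrual; the plateau results are assumptions shown as a range.

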5.4. Selection of Study Population

5.4.1. Inclusion Criteria

To be able to participate in this study, candidates must meet the following criteria at screening or other specified time point:

1. Provision of written informed consent approved by the Institutional Review Board (IRB) or Independent Ethics Committee (IEC) with privacy language in accordance with national regulations (eg, HIPAA authorization for US sites) prior to any study-related procedures, including withdrawal of prohibited medications if applicable.
2. Age ≥ 18 years or the minimum legal adult age (whichever is greater) at the time of informed consent.
3. Morphologically documented primary AML or AML secondary to myelodysplastic syndrome (MDS), as defined by World Health Organization criteria, as determined by pathology review at the study site.
4. In first relapse (with duration of remission of 6 months or less) or refractory after prior therapy, with or without HSCT. Induction therapy must have included at least 1 cycle of an anthracycline/mitoxantrone-containing induction block at a standard dose.
 - Refractory is defined as:
 - After 1 cycle, a reduction in bone marrow blasts of less than 50% and failure to achieve a CR, CRp, or CRi.
 - After 2 cycles, lack of achievement of CR, CRp, or CRi.
 - First relapse (with duration of remission of 6 months or less) is defined as:
 - Achievement of CR, CRi, or CRp, as defined by 2003 International Working Group criteria (Section 7.2) after initial AML therapy with or without consolidation or maintenance, and with or without HSCT.
 - Duration of CR, CRi or CRp is measured from the date of the bone marrow assessment which confirmed response or the date of allogeneic transplantation, to the date of the bone marrow assessment that identified relapse or the appearance of peripheral blasts.
5. Presence of the FLT3-ITD activating mutation in bone marrow or peripheral blood (allelic ratio as determined by a central laboratory with a cutoff of $\geq 3\%$ FLT3-ITD/total FLT3). If a specimen has been sent for FLT3-ITD testing at the central laboratory but the subject requires treatment for AML before the central FLT3-ITD test result is available, a local test result may be acceptable for randomization after consultation with the Medical Monitor.

6. Eligibility for pre-selected salvage chemotherapy, according to the Investigator's assessment.
7. ECOG performance score 0-2.
8. Discontinuation of prior AML treatment before the start of study treatment (except hydroxyurea or other treatment to control leukocytosis) for at least 2 weeks for cytotoxic agents, or for at least 5 half-lives for non-cytotoxic agents.
9. Serum creatinine $\leq 1.5 \times$ upper limit of normal (ULN), or glomerular filtration rate > 25 mL/min, as calculated with the Cockcroft-Gault formula.
10. Serum potassium, magnesium, and calcium (serum calcium corrected for hypoalbuminemia) within institutional normal limits. Subjects with electrolytes outside the normal range will be eligible if these values are corrected upon retesting following any necessary supplementation.
11. Total serum bilirubin $\leq 1.5 \times$ ULN.
12. Serum aspartate transaminase (AST) and/or alanine transaminase (ALT) $\leq 2.5 \times$ ULN.

5.4.2. Exclusion Criteria

Candidates will be excluded from study entry if any of the following criteria are met at screening or other specified time point:

1. Acute promyelocytic leukemia (AML subtype M3)
2. AML secondary to prior chemotherapy for other neoplasms, except AML secondary to prior MDS
3. History of another malignancy, unless the candidate has been disease-free for at least 5 years
 - Candidates with treated non-melanoma skin cancer, carcinoma in situ, or cervical intraepithelial neoplasia are eligible regardless of the time spent disease-free, if they have completed definitive treatment
 - Candidates with organ-confined prostate cancer, with no evidence of recurrent or progressive disease, are eligible if hormonal therapy has been begun, or if the tumor has been surgically removed or treated with definitive radiotherapy
4. Persistent, clinically significant $>$ Grade 1 non-hematologic toxicity from prior AML therapy
5. Clinically significant GVHD or GVHD requiring initiation of treatment or treatment escalation within 21 days, and/or $>$ Grade 1 persistent or clinically significant non-hematologic toxicity related to HSCT
6. History of or current, central nervous system involvement with AML
7. Clinically significant coagulation abnormality, such as disseminated intravascular coagulation
8. Prior treatment with quizartinib or participated in a prior quizartinib study

9. Prior treatment with a FLT3 targeted therapy including sorafenib or investigational FLT3 inhibitors (not including the multi-kinase inhibitor, midostaurin)
10. Major surgery within 4 weeks prior to screening
11. Radiation therapy within 4 weeks prior to screening
12. Uncontrolled or significant cardiovascular disease, including:
 - QTcF interval >450 msec (average of triplicate determinations)
 - Subject has bradycardia of less than 50 BPM (as determined by central reading) unless the subject has a pacemaker
 - Diagnosed or suspected long QT syndrome, or known family history of long QT syndrome
 - History of clinically relevant ventricular arrhythmias, such as ventricular tachycardia, ventricular fibrillation, or torsade de pointes
 - History of second or third degree heart block. Candidates with a history of heart block may be eligible if they currently have pacemakers, and have no history of fainting or clinically relevant arrhythmia with pacemakers.
 - Myocardial infarction within 6 months prior to screening
 - Uncontrolled angina pectoris within 6 months prior to screening
 - New York Heart Association (NYHA) Class 3 or 4 congestive heart failure
 - Left ventricular ejection fraction (LVEF) \leq 45% or institutional lower limit of normal
 - Uncontrolled hypertension
 - Complete left or right bundle branch block
13. Active infection not well controlled by antibacterial, antifungal, and/or antiviral therapy
14. Known infection with human immunodeficiency virus, or active hepatitis B or C, or other active clinically relevant liver disease
15. Unwillingness to receive infusion of blood products according to the protocol
16. In a man whose sexual partner is a woman of childbearing potential, unwillingness or inability of the man or woman to use a highly effective contraceptive method for the entire study treatment period and for at least 3 months after study treatment completion
 - Male subjects must not freeze or donate sperm starting at Screening and throughout the study period, and 105 days after the final study drug administration.
17. In a heterosexually active woman of childbearing potential, unwillingness or inability to use a highly effective contraceptive method for the entire study treatment period and for at least 3 months after study treatment completion. Additionally, for women

randomized to chemotherapy, unwillingness to adhere to the restrictions respective locally established guidelines and local approved label (prescribing information, Summary of Product Characteristics, or US product insert) from the manufacturer and the Patient Information Leaflet (package insert) as instructed by the Investigator.

- Women are not regarded as of childbearing potential if they are post-menopausal (at least 2 years without menses) or are surgically sterile (at least 1 month before study).
- Highly effective contraception methods include: hormonal methods associated with inhibition of ovulation, intra-uterine device; surgical sterilization (including partner's vasectomy) or sexual abstinence if this is the preferred and usual lifestyle of the subject.
- Female subjects must not donate or retrieve, for their own use, ova from the time of Screening and throughout the study treatment period, and for 12 weeks after the final study drug administration.

18. Pregnancy

19. Female subjects must agree not to breastfeed from the time of Screening and throughout the study period, and for 25 days after the final study drug administration.

20. Medical condition, serious intercurrent illness, or other circumstance that, in the Investigator's judgment, could jeopardize the candidate's safety as a study subject, or that could interfere with study objectives.

21. For subjects in the UK only: Refusal of permission to allow the subject's General Practitioner to be notified of their participation in the study.

